**Protocol Approved By:**

CLINICAL PRINCIPAL INVESTIGATOR:

\_\_\_\_\_  
[name]

\_\_\_\_\_  
Date

EXECUTIVE SPONSOR:

\_\_\_\_\_  
[name], MBA

\_\_\_\_\_  
Date

CO-PRINCIPAL INVESTIGATOR:

\_\_\_\_\_  
[name], MPH

\_\_\_\_\_  
Date

PROTOCOL SUMMARY	
Study Title	An evaluation of Virtual Behavioral Health Integration (VBHI) into Primary Care
Study Design	A pragmatic randomized trial evaluating total cost of care
Study Objectives	
The primary objective is to evaluate the effectiveness of the virtual behavioral health integration (VBHI) program compared to usual care, on reducing the total cost of care reimbursed from Medicare and value-based contracts within 90 days of a patient’s primary care visit.
 
Secondary objectives of the evaluation include:
 
 
• Compare demographics, Charlson comorbidity index, and social determinants of health among patients (hunger vital signs, home, education, employment, social and emotional health) between the two arms of the study
 
• Compare the 90-day acute care utilization rate after the index primary care visits
 
• Compare the 90-day primary care utilization rate after the index primary care visit
 
• Compare the pharmacy related 90-day total cost of care after the index primary care visit
 
• Stratify and report objectives by index primary care visit diagnoses (substance use disorder, depression/dysthymia, anxiety)
 
 
Exploratory analyses among patients who enrolled in the VBHI program. A subgroup of patients whose index primary care visit is within 9 months of the study start. Assessment at 3, 6, 9, and 12-months
 
 
• Symptom improvement 
 
○ Depression: 50% reduction of PHQ-9 score from initial assessment
 
○ Depression Remission: Percent of PHQ-9 scores <5 (for 2 consecutive months upon graduation)
 
○ Suicidal ideation: Percent of PHQ-9, Question #9=0 or C-SSRS negative upon graduation
 
○ Anxiety: GAD-7, 50% reduction from initial assessment
 
 
 
• Health Outcomes 
 
○ Reduction in BMI among patients with an initial BMI <math>\geq 25.0</math>
 
○ Reduction in HbA1c among diabetic patients with an initial A1c <math>\geq 9</math>
 
○ Reduction in LDL cholesterol level among patients with an initial LDL <math>\geq 160</math>
 
 
 

Inclusion Criteria	
Inclusion criteria:
 
 
• 18 years of age or older
 
• Primary care office visit at a selected site based on preventative and outpatient CPT codes
 
• Have a PHQ-9 and an overall score <math>>10</math> or Question 9 <math>>0</math>
 

	
 
• Medicare or value-based contract associated with a patient in the past year at the time of the primary care visit
 
 
Exclusion criteria:
 
 
• A patient will contribute to the analysis once using their initial enrollment to either arm of the study
 
• No insurance claim for the index primary care visit in the data warehouse upon evaluation
 


Study Procedures
	
Patients who present to participating primary care practices with an elevated patient health questionnaire (PHQ-9) score or report suicide ideation (Question 9) will be treated and followed per the proposed virtual behavioral health integration (VBHI) program or usual care. As part of the current care process, all patients with a primary care visit are given the PHQ-2 survey. A score <math>\geq 2</math> triggers the PHQ-9 survey.
 
Of the primary care practices eligible for the VBHI program, half will be randomly assigned to either the control or intervention arm. Each day a list of patients with an elevated PHQ-9 score from the prior day is generated along with the associated insurance plan for the patient. All patients who meet eligibility criteria at sites where the VBHI program is offered will be considered exposed to the intervention; whereas, patients seen at sites not utilizing the VBHI program will be considered exposed to usual care. Patients who are in the intervention arm will be treated by the behavioral health care team (licensed clinicians, health coaches, a psychiatric pharmacist and psychiatric providers). Virtual visits are conducted either by video assessment or telephonically. For the primary and secondary objectives, patients will be followed for up to 90 days after their primary care visit. For the exploratory analysis, patient with a primary care visit within 9 months of the study start date will be followed for up to 12 months after their primary care visit.
 
The VBHI program is defined by several key components:
 
 
• Introduction to the patient follow-up process
 
• Psychosocial assessment
 
• Track (Residential Movement, Nutrition, Sleep Hygiene, Stress Management, Pain Management, Perinatal/Postpartum Mood Disorders, Substance Abuse) and provide treatment recommendations
 
• Tracking of behavioral health symptoms (Depression, Anxiety, and Suicidal ideation) and provide treatment recommendations
 
• Placement into an appropriate case management program, if needed
 
• Navigation to additional psychiatric or substance use services, if needed
 
• Motivational interviewing and brief therapeutic recommendations, if needed
 

Statistical Analysis	Analyses will include all patients meeting the inclusion and exclusion criteria. Comparisons of the intervention and usual care groups will be made using univariate analyses such as the t-test and chi-square test. The primary outcome, the 90-day total cost of care, will be compared between the two groups of patients using a generalized linear mixed model. Results will be presented with odds ratios and 95% confidence intervals.
-----------------------------	--

### LIST OF ABBREVIATIONS

BHI	Behavioral Health Integration
CORE	Center for Outcomes Research and Evaluation
C-SSRS	Columbia – Suicide Severity Rating Scale
EDW	Enterprise Data Warehouse
GAD-7	Generalized Anxiety Disorder Screener
HbA1c	Hemoglobin A1c
NC	North Carolina
PHI	Private Health Information
PHQ-2	Patient Health Questionnaire - Screener for Depressive Disorders
PHQ-9	Patient Health Questionnaire – Screener for Severity of Depression
SOP	Standard Operating Procedures
VBHI	Virtual Behavioral Health Integration

## **OBJECTIVES**

### **1.1. Hypothesis**

Depressed patients who visit a primary care practice that offers a virtual behavioral health integration (VBHI) program will have lower 90-day total costs of care compared to patients receiving primary care at practices without VBHI.

### **1.2. Primary Objective**

Compare the effectiveness of the VBHI program compared to usual care, on modifying the total cost of care reimbursed by Medicare and value-based contracts within 90 days of a patient's index office visit.

### **1.3. Secondary Objectives**

For the primary and secondary objectives, patients will be followed up to 90 days.

- Compare demographics, Charlson comorbidity index, and social determinants of health among patients (hunger vital signs, home, education, employment, social and emotional health) between the two arms of the study
- Compare the patient-centric 90-day utilization rate after the index primary care visit
- Compare the 90-day primary care utilization rate after the index primary care visit
- Compare the pharmacy related 90-day total cost of care after the index primary care visit
- Stratify and report outcomes by index primary care visit diagnoses (substance use disorder, depression/dysthymia, anxiety)

### **1.4. Exploratory Analyses**

For the exploratory analysis, patients who enrolled in the VBHI program in the first 9 months from study start will have their symptoms (depression score reduction, depression remission, suicidal ideation score reduction, anxiety score reduction) and health outcomes (BMI, LDL, and HbA1c) assessed at 3, 6, 9, and 12-months.

- Symptom improvement
  - Depression: Percent of patients with a 50% reduction of PHQ-9 score from initial assessment
  - Depression Remission: Percent of patients with a PHQ-9 score <5 (for 2 consecutive months upon graduation)
  - Suicidal ideation: Percent of patients with a PHQ-9, Question #9=0 or C-SSRS negative upon graduation
  - Anxiety: Percent of patients with a 50% reduction of GAD-7 score among patients with an initial score of > 10
- Health Outcomes
  - Reduction in BMI among patients with an initial BMI  $\geq 25.0$
  - Reduction in HbA1c among diabetic patients with an initial A1c  $\geq 9$
  - Reduction in LDL cholesterol level among patients with an initial LDL  $\geq 160$

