#### 5.1.2. Rates and Variable Descriptions

- a. Demographic characteristics (age, race, gender, insurance plan)
- b. Charlson comorbidity index score

If we determine that we can identify hospital and primary care visits through claims data, we will use that as a source over using just Atrium Health encounters for the utilization rates as specified below.

- c. Patient-centric defined 90-day utilization rate. This is a utilization rate among patients with an ED, inpatient, or observation encounter to any Atrium Health facility ( $\leq 90$  days after the primary care visit).
- d. The 90-day primary care utilization rate. This is a utilization rate among patients with a primary care encounter ( $\leq 90$  days after the primary care visit).
- e. Primary care visit
  - i. At least one CPT code for preventative or outpatient visit
- f. Pharmacy related 90-day total cost of care. The pharmacy total cost of care is defined as the summation of all pharmacy paid claims within 90 days of the primary care visit among patients with pharmacy claim data ( $\leq 90$  days after the primary care visit).

Symptom and health outcomes are assessed at 3, 6, 9, and 12-months among patients who enrolled in the VBHI program.

- g. Asses symptom improvement for depression
  - i. Pre- PHQ-9 score from primary care visit
  - ii. Post- PHQ-9 score
- h. Primary care visit diagnoses (primary or secondary billed diagnoses)
  - i. substance use disorder
  - ii. depression/dysthymia
  - iii. anxiety
- i. Anxiety
  - i. Pre- GAD-7 score from initial enrollment
  - ii. Post- GAD-7 score

- j. Suicidal ideation
  - i. Pre- PHQ-9, Q9 score from primary care visit
  - ii. Post- PHQ-9, Q9 score
- k. Remission of depressive symptoms
  - i. PHQ-9 less than 5 in 2 consecutive months
- l. BMI
  - i. Pre- BMI level from primary care visit
  - ii. Post- BMI level
- m. HbA1c among diabetic patients
  - i. Pre- A1c level from primary care visit
  - ii. Post- A1c level
- n. LDL cholesterol level
  - i. Pre- LDL level from primary care visit
  - ii. Post- LDL level
- o. Hunger vital signs – reported upon enrollment
  - i. Within the past 12 months, we worried whether our food would run out before we got the money to buy more?
  - ii. Within the past 12 months the food we bought just didn't last and we didn't have the money to get more?
- p. Home – reported upon enrollment
  - i. What is your housing situation today?
  - ii. Are you worried about losing your house?

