## 5.2. Virtual Behavioral Health Integration

The flow of patients from initial contact to their follow-up calls is outlined in Appendix 1. In the existing VBHI primary care workflow, all patients are given the PHQ-2 survey. A score  $\geq 2$  triggers the PHQ-9 survey. The following day the behavioral health team receives a patient report. The report

includes patients seen the prior day at intervention sites that had an elevated PHQ-9 score >10 or reported suicide ideation (Question 9 >0). The Monday report includes patients seen Friday-Sunday. Patients associated with Medicare or other value-based insurance plan are identified in the report. The behavioral health care team will reach out to these patients for enrollment utilizing video assessment or telephonic outreach. The patient always has the option not to be followed by the behavioral health care team.

The behavioral health care team will complete the initial behavioral health assessment. The initial health assessment contains information such as preferred communication method, GAD-7, psychiatry provider, collateral resources, recent ED and hospital utilization, substance use disorder, medication barriers, appointment barriers, community resources, and crisis planning.

The frequency of follow-up assessments depends on the clinical presentation and medication recommendation and/or adherence. The assessment includes information such as a suicide ideation safety screening, an appointment reminder, appointment barrier evaluations, medication reconciliation, medication obtainment follow-up, substance use disorder follow-up, supportive listening, psychoeducation, community resource follow-up, and additional crisis planning.

The Columbia-Suicide Severity Rating Scale (C-SSRS) helps identify whether someone is at risk for suicide, and the severity and immediacy of the risk. It also identifies level of support the person needs. The screening tool is administered during each phone contact to measure suicide ideation. Follow-up patients enrolled in the VBHI program will receive follow-up phone calls. The frequency of calls is dependent on the clinical presentation and medication recommendation and/or adherence. A follow-up assessment is completed upon each phone call.

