#### 5.4. Patient Graduation from the VBHI Program

- Reached max benefit as deemed by the behavioral health care team
- Depression remission – PHQ-9 <5 for 2 consecutive months
- Unable to connect: 4 calls attempted over 12 days
- Transition to lower level of care
  - Patients who transition to a primary care clinic not utilizing VBHI services
  - Moved out-of-state
  - Discharged from primary care clinic utilizing VBHI services
- Transition to higher level of care
  - Psychiatry/Treatment Program
- Patient states that they are no longer interested in services but their last PHQ-9 >5
- Declined or no longer interested in services
- Death

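### The exploratory suicidal-ideation outcome is defined in conflicting ways, and as worded in the objectives it can be met without any change in ideation

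*Combined protocol and SAP*

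**What the plan says.** The objectives (section 1.4, repeated in the Protocol Summary) report the percentage of patients with "Question #9=0 or C-SSRS negative upon graduation". The lead-in to section 1.4 calls this outcome a score reduction, and places it at 3, 6, 9 and 12 months among patients who enrolled in VBHI in the first 9 months.

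The variable list (section 5.1.2, item j) names one instrument at both times: "Pre- PHQ-9, Q9 score from primary care visit" and "Post- PHQ-9, Q9 score". The C-SSRS does not appear there. Section 6.2 models change from baseline to the four fixed times with a binary dependent variable.

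The C-SSRS is nevertheless collected in the program. Section 8.1 lists it in the initial assessment, and section 5.2 says of follow-up: "The screening tool is administered during each phone contact to measure suicide ideation".

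Graduation (section 5.4) is not a single event. Its routes include depression remission, maximum benefit, transfers and death, and also "Unable to connect: 4 calls attempted over 12 days", "Declined or no longer interested in services" and "Patient states that they are no longer interested in services but their last PHQ-9 >5".

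Eligibility (section 4.3.1) is a PHQ-9 total above 10 or a Question 9 score above 0, so a patient can enter with Question 9 equal to 0.

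**The concern.** One outcome has two instrument rules and two timing rules, and the analysis section does not choose between them. Two analysts could follow the protocol and report different percentages.

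The version in the objectives is also the lenient one. It is a status at exit, not a change. It can be reached through either of two instruments, and it is not restricted to patients who had ideation at the start. Section 11 commits to a final report and a manuscript on outcomes. A figure for resolved ideation that includes patients still endorsing Question 9, or patients who never endorsed it, would mislead readers about a group that section 10 describes as high risk.

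**Working it through.** The plan gives no rate, sample size or power for this outcome, so there is no figure to reproduce. The check has three parts.

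**1. The definitions side by side**

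| Place | Instrument at follow-up | Timing |
|---|---|---|
| Protocol Summary; 1.4 bullet | Question 9 or C-SSRS | at graduation |
| 1.4 lead-in | not named; a score reduction | 3, 6, 9, 12 months |
| 5.1.2, item j | Question 9 only | 3, 6, 9, 12 months |
| 6.2 | not named; binary | 3, 6, 9, 12 months |

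Instrument and timing both conflict. The neighboring outcomes in section 1.4 are restricted to patients abnormal at the start (GAD-7 above 10, BMI at least 25.0, HbA1c at least 9, LDL at least 160). The ideation outcome has no such restriction.

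**2. What the either/or rule reports when nothing changes**

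Let q be the share of analyzed patients with baseline Question 9 above 0, and c the share of those who are C-SSRS negative. Neither is in the documents; both are assumed over a range. With Question 9 unchanged in every patient:

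- Question 9 alone: met = 1 − q
- Either instrument: met = (1 − q) + q × c
- Added by the second instrument: q × c

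| q | c | Question 9 alone | Either instrument | Added (points) |
|---|---|---|---|---|
| 0.3 | 0.1 | 70% | 73% | 3 |
| 0.3 | 0.5 | 70% | 85% | 15 |
| 0.5 | 0.3 | 50% | 65% | 15 |
| 0.8 | 0.3 | 20% | 44% | 24 |
| 1.0 | 0.1 | 0% | 10% | 10 |
| 1.0 | 0.5 | 0% | 50% | 50 |

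There are two separate effects. The term 1 − q comes from patients who had no ideation on Question 9 at the start, and arises under either instrument rule. The term q × c comes from the second instrument. Restricting to baseline-positive patients (q = 1) and using Question 9 at both times removes both: with no change, the reported rate is 0%.

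**3. Timing at graduation**

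Remission is itself a graduation route in section 5.4, and section 1.4 scores remission "for 2 consecutive months upon graduation". Whoever leaves by that route meets the remission outcome by definition and is selected for a low PHQ-9 total, of which Question 9 is a part. Measuring at graduation therefore depends on the outcome.

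The effect of lost or declining patients is different. Assume 40% are unmeasured and 60% of those measured meet the outcome:

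- Observed cases: 60%
- Unmeasured counted as not met: 0.60 × 0.60 = 36%
- True rate if the unmeasured have a 30%, 60% or 80% rate: 0.36 + 0.40 × 0.30 = 48%; 0.36 + 0.40 × 0.60 = 60%; 0.36 + 0.40 × 0.80 = 68%

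The reported figure can be too high or too low, depending on a counting rule that the plan does not state.

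**The case against.** The strongest defense is that the analysis-level text is sound. Item j is consistent within itself, with Question 9 before and after, and section 6.2 already uses the fixed times. On this view the graduation wording is a leftover in the objectives. The word joining the two instruments could also mean whichever is available, since the C-SSRS is given by phone. The C-SSRS is collected at the initial assessment, so a like-for-like comparison on that scale is possible.

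Much of this stands, and it makes the repair easy. It does not remove the conflict. The objectives are where the outcome is stated, no section ranks one definition above another, and no rule says which instrument prevails when both are available and disagree. Item j also leaves open the patient whose Question 9 score was 0 at entry.

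A reader might infer that counting lost and declining patients as graduates builds improvement into the result. The documents do not support that. Section 1.4 speaks of a percentage of enrolled patients; if the unmeasured stay in the denominator, they lower the rate. Nor can it be said that these patients have no exit score: one declining route is defined by the last PHQ-9, and the C-SSRS is given at each phone contact. What is missing is a rule for which value counts.

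**Conclusion.** The point holds as a conflict of definitions with a bias of known direction in one part. The either/or rule can never give a lower rate than Question 9 alone. With no true change it adds q × c, which is 3 to 50 points over the assumed ranges of q (0.3 to 1.0) and c (0.1 to 0.5). Those ranges are illustrative, so the span shows what is possible and does not estimate what the trial will see. The unrestricted denominator adds a further 1 − q of patients counted as met without change. Graduation is an outcome-dependent time because remission triggers it. No direction can be given for lost or declining patients.

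This is a minor point. The outcome is exploratory, and neither the primary cost comparison nor its conclusion depends on it.

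**What to change.** Reconcile the Protocol Summary, section 1.4 and section 5.1.2, item j, as follows:

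- Define the outcome as Question 9 equal to 0 among VBHI enrollees whose Question 9 score at the index visit was above 0.
- Assess it at 3, 6, 9 and 12 months, and drop graduation as the time of measurement.
- Report the C-SSRS as a separate outcome, compared with the C-SSRS from the initial assessment in section 8.1, and give the number of patients in whom the two instruments disagree.
- At each time, show the rate over all baseline-positive enrollees, with unscored patients counted as not met, beside the rate among those scored. Neither is right in general; together they show how much depends on missing scores.

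The cost is revised wording and one extra table. The instruments and the assessment times are already in the plan. The denominator will be smaller, and the reported success rates will be lower.

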## 2. BACKGROUND

Mental illness is highly prevalent among adults with reports as high as 20% and a common reason for visits to primary care. Affective disorders like depression and anxiety generate significant healthcare costs and result in social and vocational disability. Almost half of patients who are treated for major and minor depression are seen exclusively in primary care, with another 20% to 30% treated in both specialty and primary care settings.

Mental health treatment among primary care practices is typically delivered through short episodes of care. Primary care providers tend to offer less intensive mental health treatment than that provided by psychiatrists. The level of involvement of primary care providers to deliver outpatient mental health care often depends on: (1) lack of mental health providers in the region; (2) willingness to prescribe psychotropic medications; and (3) knowledge of mental health disorders. Clinical implications of a mental illness comorbidity include increased risk of suicide, psychiatric hospitalization, increased disability, decreased compliance with treatment of medical illness, and markedly increased utilization of medical services. If untreated, depression and anxiety disorders can contribute to high medical utilization. It has been reported that 24% percent of the top 10% (high) healthcare utilizers have a diagnosis of current major depression and 22%, from an anxiety disorder.

Mental health providers have increasingly targeted their efforts on delivering virtual psychiatric consultation in the primary care setting. Use of virtual care programs providing mental health services is on the rise, often in rural and underserved areas where access to mental health services is not present or limited. Telepsychiatry efforts are often also implemented to improve rural providers' capacity for managing patients with mental health illnesses. Outpatient psychiatric consultation programs have utilized clinicians to conduct telephone consultations as an efficient means to provide consultative, supplemental, and follow-up care. Evidence has shown that telepsychiatric evaluation services can be economical and with levels of quality and patient satisfaction similar to those found with face-to-face evaluations. Few programs, however, have reported on efforts to integrate these multiple services into a comprehensive "virtual mental health clinic" that can both provide a wide range of clinical services and support providers by means of educational offerings. No studies to date have shown through a rigorous evaluation the effect of virtual behavioral health integration on total cost of care that include value-based contracts. The proposed virtual behavioral health integration (VBHI) program into the primary care setting is a structured mental illness treatment program that includes both behavioral treatment and counseling components aimed at reducing cost of care, developing and sustaining adaptive coping strategies, and improving short term acute care utilization.

